10.6 Assessment of Expectedness

The Chief Investigator for the DREAM trial is responsible for determining whether a safety event is expected or unexpected. There is no requirement for a reporting investigator to make an assessment of expectedness.

An event will be considered 'unexpected' if it is not listed within the current and approved protocol (see section 10.6.1) for the study at the time of the event's onset. The nature, severity, or frequency of the event should be considered – if this is not consistent with that described for the type of event in the protocol the event should be assessed as unexpected.

10.6.1 Reference Safety Information (RSI)

The RSI in DREAM is detailed in Table 4: Expected Events

Table 4: Expected Events

Event	
Anaphylaxis	
Urticaria	
Exacerbation of eczema	
Allergic reaction	
Acute bronchospasm (asthma)	

10.7 Notes on Adverse Event Inclusions and Exclusions

The following events must be recorded for the purposes of the trial:

- An exacerbation of a pre-existing illness.
- An increase in frequency or intensity of a pre-existing episodic event/condition.
- A condition (even though it may have been present prior to the start of the trial) detected after trial treatment.
- Continuous persistent disease or symptoms present at baseline that worsens following the administration of the study/trial treatment.
- Laboratory abnormalities that require clinical intervention or further investigation (unless they are associated with an already reported clinical event).
- Abnormalities in physiological testing or physical examination that require further investigation or clinical intervention.
- Injury or accidents.

Do not record:

- Medical or surgical procedures the condition which leads to the procedure is the adverse event.
- Pre-existing disease or conditions present before treatment that do not worsen.
- Situations where an untoward medical occurrence has occurred e.g. cosmetic elective surgery*.
- Overdose of medication without signs or symptoms**
- The disease being treated or associated symptoms/signs unless more severe than expected for the patient's condition

* Elective surgery is cited here as example of an event that is not reportable as an AE.

[figure not shown]
** See also section 10.12.1. If overdose occurred with resulting signs and symptoms that met the protocol criteria for AEs or /SAEs/ then they should be reported accordingly. This bullet is to note that though overdose of medication without signs or symptoms may be excluded from AE reporting this may still require investigation to ensure the protocol and regulatory requirements are met e.g. for IMP management and administration to ensure participant safety.

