3.3 Hypotheses and Objectives

The primary hypothesis is that one year feeding with pHF will be more efficacious than with eHF in the treatment of 6–12 month-old infants with IgE-mediated CMA.

Secondary hypotheses are that:

- 1. one year feed with pHF will be as safe as with eHF for 6-12 month-old infants with IgE-mediated CMA
- 2. one year feeding with pHF will be more efficacious than with eHF in inducing CM desensitisation for 6-12 months old *pHF-tolerant* infants with IgE-mediated CMA
- 3. one year feeding with pHF will be more efficacious than with eHF in inducing CM desensitisation for 6-12 months old *pHF-reactive* infants with IgE-mediated CMA
- 4. infants who cannot tolerate pHF at the start of the study, will be able to tolerate it after a short Oral Immunotherapy Treatment (OIT) regimen to pHF

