8.7.4 Double-blind Placebo Controlled Food Challenge (DBPCFC) 8.7.4.1 VISIT 8 (DBPCFC Day 1)

Visit 8 will be conducted 48 weeks (+/- 2 weeks) from randomisation. This visit entails Day 1 of the DBPCFC, to CM product as per the trial DBPCFC SOPs. Participants will be monitored by a delegated clinician, supported by delegated nurse(s) and will remain in the department for up to 8 hours, as appropriate. In rare cases and if they experience severe anaphylaxis, they may need to be hospitalised overnight, as per the clinical judgment of the clinician.

- 1. Confirm continuation of participation.
- 2. Physical Examination, current medical history & vital signs: Weight, length, EASI Score & history of wheeze. The following will be confirmed to be normal and a statement to this effect recorded in the medical notes: general physical examination with chest auscultation, Peripheral arterial pulse, heart rate, systolic and diastolic blood pressure, respiratory rate, and oxygen saturation.
- 3. Skin prick tests: will be conducted for cows' milk using whole, fresh milk, egg, House Dust Mite mix, cat dander, 6 grass pollen mix.
- 4. Blood sample for Antigen-specific IgE to the following Antigens: IgE levels to CM (CM-IgE), Alpha lactalbumin (ALA-IgE), beta lactoglobulin (BLG-IgE), and casein (Cas-IgE).
- 5. Collection of Buccal samples, blood samples and stool samples for storing: These will be collected only where **consent** has been provided, before the start of the challenge and stored locally until transferred to the central laboratory.
- 6. Challenge Day 1: Will be conducted as per the trial DBPCFC SOPs. Results of the DBPCFC must be recorded in the **participant's medical notes**.
- 7. Collect diary from previous visit: Collect completed diary pages from previous visit and review. Any new AEs will be recorded in the participant's medical notes and on the AE Log and any previous AEs will be followed-up and marked as resolved if appropriate.
- 8. Provide diary and instructions for use: Give participants diary and instructions for filling in.
- 9. Record AEs: Any AEs occurring from this visit must be recorded in the participant's medical notes and on the AE Log (see section 10).
- 10. Request for any unused tins to be returned at the next visit: Ask parents to return any unused tins at the next visit.

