10 SAFETY REPORTING

10.1 Time Period for Active Monitoring of Safety Events

The "active monitoring" of all safety events experienced by trial participants will be from randomisation until 48 hours after visit 9.

Any additional information on selected adverse events related to the initial challenges, will be captured in the Challenge Form (see sections 8.4.1.2 and 8.4.1.3). Expected adverse events during the challenges will not be included in the adverse events log, but rather in the challenge logs.

Any safety events occurring *after* the end the active monitoring period that meet the definition of **serious** (see section 10.3) must continue to be reported by sites to the LCTC in accordance with the timeframes and procedures described in section 10.9.

Upon becoming aware of a serious adverse event (SAE/Related SAE/RUSAE), the investigator or other delegated member of the site team must report this to the LCTC **within 24 hours**.

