10.9.1 Flowchart for Reporting Requirements of Adverse Events

10.9.2 Reporting Safety Events

All safety events (whether or not assessed as serious / related / expected) should be recorded on an AE form; multiple events can be recorded on one form.

Safety events that are assessed as "serious" must **also** be recorded in more detail on an SAE Form; a single form is used for each individual event (i.e. a single diagnosis), though multiple symptoms can be recorded. Each SAE should have a corresponding record on the participant's AE form.

Additional information should be provided on a follow-up form and sent to LCTC within 5 days if the serious event has not resolved at the time of the report.

SAE Forms collect data regarding the nature of event, date of onset, severity, corrective therapies given, outcome and causality; all serious events reported to LCTC will be reviewed by the CI or authorised delegate and assessed for causality and expectedness.

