11.5 Analysis Plan

The trial will be analysed using the International Conference on Harmonisation E9 guidelines and reported using the 'Consolidation Standard of Reporting Trials' (CONSORT) guidelines.

The analyses of primary and secondary outcomes will use the principle of intention to treat, based on all the randomised participants, as far as is practically possible. A p-value of 0.05 or less will be used to declare statistical significance for all analyses and results will be presented with 95% confidence intervals. Baseline characteristics will be presented but no comparisons will be undertaken, rather the clinical importance of any imbalance will be noted.

Binary data (including the primary outcome of the proportion of patients who are no longer allergic to CM protein) will be reported in terms of relative risk and analysed using logistic regression, adjusted for the stratification factors (site and initial tolerance to pHF). There will be a secondary analysis of the primary outcome using a chi-squared test for consistency with the sample size calculation. There will also be two subgroup analyses of the primary outcome, the first will include patients who initially tolerate pHF and the second will include patients who did not initially tolerate pHF.

Continuous data will be presented as means and standard deviations and analysed using two-sample t-tests (if data is skewed, medians and ranges will be presented, and analysis will be by Mann Whitney U tests). All related AEs and serious adverse events SAEs reported by the clinical investigator will be presented, identified by treatment group, but no formal comparisons will be made across the treatment groups.

Missing data will be monitored, and strategies developed to minimise its occurrence, however as much data as possible will be collected about the reasons for missing data and this will be used to inform the handling of missing data.

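### Section 10.7 can be read to keep non-serious allergic reactions to the study formula off the AE record, and it is unclear where final-challenge reactions are logged

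*Protocol*

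**What the plan says.** **Recording rules.** Section 10.7 tells sites not to record, among other things: "The disease being treated or associated symptoms/signs unless more severe than expected for the patient's condition". The same section requires recording of "An increase in frequency or intensity of a pre-existing episodic event/condition", and of existing illness or symptoms that get worse once treatment has started. Section 10.9.2 is broader: "All safety events (whether or not assessed as serious / related / expected) should be recorded on an AE form". Table 4 (section 10.6.1) lists anaphylaxis, urticaria, eczema exacerbation, allergic reaction and bronchospasm as expected events. Section 3.2.1.1 names allergic reactions during OIT and free feeding among the risks.

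**Challenge reactions.** Section 10.1 first says: "Any additional information on selected adverse events related to the initial challenges, will be captured in the Challenge Form". It points there to the sections on visits 2 and 3. The next sentence reads: "Expected adverse events during the challenges will not be included in the adverse events log, but rather in the challenge logs". The visit 8 instructions say: "Any AEs occurring from this visit must be recorded in the participant's medical notes and on the AE Log", with a cross-reference to section 10, and visit 9 repeats this. The AE endpoint (section 3.4.2, item 9) runs to V9. Table 1 (section 10.2) defines a related AE by reference to any research procedure, not only the formula.

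**Hypothesis and analysis.** Secondary hypothesis 1 (section 3.3) is that "one year feed with pHF will be as safe as with eHF for 6-12 month-old infants with IgE-mediated CMA". Section 11.5 presents related AEs and SAEs by treatment group, "but no formal comparisons will be made across the treatment groups".

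**The concern.** The signs of the disease being treated are the same events that the study formula is expected to provoke. A site that follows the 10.7 bullet literally could leave a hive or mild reaction after a feed off the AE form because it is no worse than milk allergy would predict. Section 9.1 says that pHF is more allergenic than eHF and has no indication for milk-allergic infants, so lost events would come mainly from the pHF arm. An event that was never written down cannot be restored by the SAP, and the list of safety events that goes to the IDSMC (section 10.12) contains only what was recorded.

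The second issue is distinct. The DBPCFC is the efficacy test, and if pHF works, more eHF infants will react to it. If those reactions enter the AE log as related to a research procedure, an efficacy benefit can show up as a safety benefit.

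Third, a hypothesis of equal safety needs some stated way of judging it. The protocol gives neither a margin nor a formal comparison.

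**Working it through.** **1. The recording texts side by side.** Take a first non-serious urticaria after a study feed. Under the 10.7 exclusion it is a sign of the treated disease and is omitted unless worse than expected. Under the 10.7 inclusion bullets it may count as a more frequent or more intense episode and is recorded. Under 10.9.2 it is recorded whether or not expected. The texts give different answers, and no reference severity is supplied for judging what is more than expected. Section 10.9.2 does not clearly override 10.7, because 10.9 opens by applying its procedures to events that are recorded for the study, so 10.7 can be read as a prior filter. Serious events are outside this problem: sections 10.1 and 10.11 require them within 24 hours.

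**2. What each reading does to the AE log.**

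| Reading applied by the site | Formula reactions, non-serious | DBPCFC reactions |
|---|---|---|
| 10.7 exclusion throughout | can be lost, mainly pHF | also excluded |
| 10.9.2 and the V8/V9 text throughout | kept | added |
| 10.9.2 for feeding, 10.1 for the DBPCFC | kept | in challenge log |
| 10.7 exclusion for feeding, V8/V9 text for the DBPCFC | can be lost, mainly pHF | added |

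Only the last, mixed reading produces both distortions.

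**3. The plan's own figure.** Section 11.3 assumes tolerance of 0.35 (eHF) and 0.60 (pHF), two-sided alpha 0.05 and 90% power.

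n = [1.960 × √(2 × 0.475 × 0.525) + 1.2816 × √(0.35 × 0.65 + 0.60 × 0.40)]² / 0.25² = (1.384 + 0.876)² / 0.0625 ≈ 81.8, so 82 per arm. Then 82 / 0.8 = 102.5, so 103 per arm and 206 in total. Both stated figures reproduce.

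**4. DBPCFC reactors at those rates.** Reactors = n × (1 − tolerance rate).

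- 82 per arm: 82 × 0.65 = 53.3 eHF and 82 × 0.40 = 32.8 pHF, a difference of 20.5.
- 103 per arm: 66.95 and 41.2, a difference of 25.75.

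These are upper figures. They treat every non-tolerant infant as a reactor, whereas section 8.8.1 has an inconclusive category. If the challenge log is used, the contribution to the AE log is 0.

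**5. Illustration of pooling.** The document gives no feeding-reaction rates, so these are assumptions, with feeding and challenge reactions taken as independent. Share with at least one event = 1 − (1 − feeding rate) × (1 − challenge rate).

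| Assumed feeding rate, eHF / pHF | True difference (pHF − eHF) | Pooled eHF / pHF | Pooled difference |
|---|---|---|---|
| 0% / 5% | +5 points | 65.0% / 43.0% | −22 |
| 5% / 30% | +25 points | 66.75% / 58.0% | −8.75 |
| 5% / 50% | +45 points | 66.75% / 70.0% | +3.25 |

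The pooled sign turns when the pHF rate exceeds 1 − (1 − eHF rate) × 0.35 / 0.60. That is 42% for an eHF rate of 0% and 53% for an eHF rate of 20%.

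**6. Precision for a safety difference.** Half-width of the 95% CI = 1.96 × √(2p(1 − p)/n), with the event rate p assumed equal in both arms.

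| p | n = 103 | n = 82 |
|---|---|---|
| 5% | ±6.0 points | ±6.7 |
| 10% | ±8.2 | ±9.2 |
| 30% | ±12.5 | ±14.0 |

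For scale, a non-inferiority comparison with 10% in both arms, one-sided 0.025 and 90% power needs (1.960 + 1.2816)² × 2 × 0.1 × 0.9 / margin² per arm: 190 for a 10-point margin and 85 for a 15-point margin.

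**The case against.** A reader might infer that the rules jointly bias safety towards pHF, removing its feeding reactions while adding eHF challenge reactions. The documents do not support that. A site that applies the 10.7 exclusion consistently would also leave out ordinary DBPCFC reactions, which are the plainest sign of the treated disease. A site that follows 10.9.2 would keep the feeding reactions. Stacking needs the exclusion to be applied at home and ignored at V8 and V9.

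Nor is it settled that DBPCFC reactions are logged as AEs. Section 10.1 refers to challenges in general terms, and the V8/V9 instruction defers to section 10 and is also used at V4 to V7. What stands is the ambiguity, since the preceding sentence in 10.1 concerns only the initial challenges.

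It is also fair to say that several safeguards pull towards recording: the other 10.7 bullets, the review of diaries for AEs at visits, and telephone questions about allergic episodes and other AEs. They make systematic loss less likely, but they do not remove the written instruction to omit.

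It would be wrong to say that safety is never compared. Section 11.5 shows related AEs and SAEs by group, and only formal comparison is ruled out. Descriptive safety reporting is legitimate and serves the objective of evaluating safety (section 3.3.2). It does not match the hypothesis as worded. Finally, a 25-point challenge excess does not simply cancel a 25-point feeding excess, because participant-level risks do not add; step 5 shows this.

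**Conclusion.** The core point holds. The 10.7 bullet conflicts with 10.9.2 and with its own list, on the events that matter most for the safety of pHF. The exposure is limited to non-serious reactions. Any loss would fall mainly on pHF and would be irreversible, which alone justifies an amendment. How many events would be lost cannot be derived, since the protocol gives no feeding-reaction rates.

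The DBPCFC point is conditional: up to about 53 eHF versus 33 pHF infants of 82 per arm if reactions are logged as related AEs and every non-tolerant infant reacts, fewer with inconclusive challenges, and none if the challenge log is used. It is a risk that depends on how sites read the text, not a demonstrated bias.

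The equal-safety hypothesis has no margin and no matching comparison. At an assumed event rate of 10% the trial could estimate a difference to within about 8 to 9 points, so an estimation statement fits it better than a claim of equal safety. The primary outcome is unaffected.

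**What to change.** - **Section 10.7:** delete the bullet on the disease being treated. Alternatively, add that allergic reactions, urticaria, eczema exacerbation, bronchospasm and anaphylaxis of any severity after randomisation are always recorded, and that this overrides the rest of the list.
- **Sections 10.1, 8.7.4.1, 8.7.4.2 and 10.9.2:** state explicitly that the challenge-log rule applies to V8 and V9, and align the visit text and 10.9.2 with it. Leave SAE reporting as it is.
- **Reporting:** tabulate DBPCFC-day reactions separately from formula-feeding reactions.
- **Sections 3.3 and 11.5:** present the proportion with any allergic reaction by arm, with a risk difference and 95% CI, or reword hypothesis 1 as descriptive estimation.

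The cost is a short amendment, somewhat more AE forms for sites and one extra table. The changes concern recording and reporting only, not clinical management. The 10.7 change is the urgent one, because events missed before it takes effect cannot be recovered at analysis.

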10.8 Notification of Deaths

If the research team become aware of the death of a participant (whether related to the trial or not) this should be notified to the LCTC using SAE form within **24 hours** of becoming aware.

10.9 Reporting Procedures

All safety events that are recorded for the study should be reported following the procedures detailed below. The occurrence of a safety event may come to the attention of research staff during routine study visits, from the participant's notes, directly from the parent or by other means. Note that reporting procedures vary dependent on the nature of the incident (i.e. "serious" events are to be reported to LCTC in an expedited manner). Any questions concerning adverse event reporting should be directed to the LCTC in the first instance. A flowchart is given below to aid in determining reporting procedures for different types of adverse events.

10.9.1 Flowchart for Reporting Requirements of Adverse Events

10.9.2 Reporting Safety Events

All safety events (whether or not assessed as serious / related / expected) should be recorded on an AE form; multiple events can be recorded on one form.

Safety events that are assessed as "serious" must **also** be recorded in more detail on an SAE Form; a single form is used for each individual event (i.e. a single diagnosis), though multiple symptoms can be recorded. Each SAE should have a corresponding record on the participant's AE form.

Additional information should be provided on a follow-up form and sent to LCTC within 5 days if the serious event has not resolved at the time of the report.

SAE Forms collect data regarding the nature of event, date of onset, severity, corrective therapies given, outcome and causality; all serious events reported to LCTC will be reviewed by the CI or authorised delegate and assessed for causality and expectedness.

10.10 Follow-up After Adverse Events

All AEs should be followed until satisfactory resolution or until the investigator responsible for the care of the participant deems the event to be chronic or the patient to be stable.

When reporting SAEs the investigator responsible for the care of the participant should apply the following criteria to provide information relating to event outcomes:

- resolved;
- resolved with sequelae (specifying with additional narrative);
- not resolved/ongoing;
- ongoing at final follow-up;
- fatal or unknown.

10.11 Safety Reporting Responsibilities – Investigator

The PI is responsible for ensuring all safety events that are observed or recorded during the study are reported to LCTC, regardless of their relationship to trial treatment. It is the responsibility of the PI/Co-Investigator (medically qualified person) as recorded on the Delegation Log, to assess the seriousness and causality of events.

All safety events must be recorded on an AE form and transferred to LCTC within 7 days of the site team becoming aware of the event.

Safety events that meet the definition of "serious" must be reported in more detail to the LCTC on an SAE form and reported **immediately and in no circumstances later than 24 hours from becoming aware**, where they will be appropriately processed.

The SAE form should be completed by an appropriately delegated member of the research team; the assessments of seriousness and causality must be performed by an appropriately medically qualified person. Minimum reporting information must be provided in initial reports for all studies.

Minimum information required for reporting:

- Sponsor study number
- One identifiable coded subject
- One identifiable reporter
- One SAE
- A causality assessment
- A description of circumstances

N.B. In the absence of a delegated medically qualified person the form should be completed and signed by an alternative member of the research site trial team and submitted to the LCTC. As soon as possible thereafter the responsible investigator should check the SAE form, make amendments as appropriate, sign and re-send to the LCTC. The initial report shall be followed by detailed follow-up reports as appropriate. Safety events should be reported to the site R&D team in accordance with local policy.

10.11.1 Reporting an Initial or Follow-Up SAE

The investigator should ensure the actions below are completed for all reportable SAEs:

- i. Research sites should telephone the appropriate trial manager / data manager on [contact]** to advise that an SAE report has been submitted as soon as possible.
- ii. The SAE form should be transferred SECURELY to [contact] (within 24 hours).
- iii. The responsible investigator must notify their R&D department of the event (as per standard local governance procedures).
- iv. The patient must be identified by trial number, age or month and year of birth and initials **only**. The patient's name **must not** be used on any correspondence.
- v. SAEs must be subsequently followed up in line with the processes below:
 - a. Follow up must continue until clinical recovery is complete and laboratory results have returned to normal, or until the event has stabilised.
 N.B. Follow-up may continue after completion of protocol treatment if necessary.
 - Follow-up information is noted on a new SAE form to be transferred securely to the LCTC as soon as more information becomes available.
 - c. Tick the appropriate box on the new SAE form to identify the type of report; this is dependent on resolution status of the SAE e.g. follow-up / final.
- vi. Extra, annotated information and/or copies of anonymised test results may be provided separately.

Patient safety incidents that take place in the course of research should be reported to the National Reporting and Learning System (NRLS) by each participating NHS Trust in accordance with local reporting procedures.

